**Study Group 2 Only (A7=2)**

L9. How do you think you may have become infected with HBV?

---

**READ and HEARD:** *Thank you for taking the time to complete this questionnaire. If you have any questions or concerns, please talk to the research assistant or nurse. You can also contact the medical director at our blood bank.*

**READ and HEARD:** *You have finished the questionnaire. From now on, please do not touch the computer or screen. Please, talk to the research assistant, the person who assisted you at the beginning of this questionnaire. This assistant will close the screen and acknowledge you for your participating in this study.*

**ETIME = ENDTIME - STARTTIM**

## Appendix 8 Objective 3 Brief Clinical Questionnaire

*This section of the form is to be completed by the research assistant or other research staff.*

A1. Participant ID (*Internal study number to be assigned by Study Management System*)

\_\_\_\_\_

A2. Participant Donor Number (*Number that will link with donor's Meditech info*)

\_\_\_\_\_

A3. Location of Study Visit. (*Blood collection site neumonic (clinic site code). The neumonic can be mapped back to Branch, Zone or Province - this will have to be coded during analysis phase*)

\_\_\_\_\_

A4. Date of Study Visit (DD/MM/YYYY)

\_\_\_\_\_

A5. Research Staff Initials: \_\_\_\_\_

**CURRENT MEDICAL STATUS**

B1. Since your last visit for participation in this study have you gone to your doctor or sought medical care at a clinic or hospital?

0 No **Skip to B2**

1 Yes

97 Don't Know

98 Refuse to Answer

B1a. If yes, what was the reason for seeking medical care? \_\_\_\_\_  
\_\_\_\_\_

B2. Since your last visit for participation in this study have you gone to a traditional healer?

0 No **Skip to B3**

1 Yes

97 Don't Know

98 Refuse to Answer

B2a. If yes, what was the reason for seeing the traditional healer? \_\_\_\_\_  
\_\_\_\_\_

B3. Since your last study visit have you had a cold, flu, or any other infection?

0 No **Skip to B4**

1 Yes

97 Don't Know

98 Refuse to Answer

B3a. If yes, what symptoms did you have? Please list all the symptoms you can think of such as headache, fever, body pain, chills, vomiting, diarrhea, or any other symptom that you may have had. \_\_\_\_\_  
 \_\_\_\_\_

B4. Since your last study visit have you started taking antiretroviral medicines, also known as ARVs?

- 0 No **Skip to B6**
- 1 Yes
- 97 Don't Know
- 98 Refuse to Answer

B4a. What are the names of the antiretroviral (ARV) medicines you are currently taking? \_\_\_\_\_  
 \_\_\_\_\_

To help trigger your memory, please look at the placard with pictures of medicines and then place a check mark in the box next to the medications that look like the ones you are taking:

Place ✓ if taking this medication	Medication
	AZT - Zidovudine
	ddI - Didanosine
	3TC - Lamivudine
	D4T - Stavudine
	ABC - Abacavir
	TDF - Tenofovir
	FTC - Emtricitabine
	IDV - Indinavir
	NVP - Nevirapine
	EFV - Efavirenz
	ETV - Etravirine
	ATV - Atazanavir
	LPV/r - Lopinavir/Ritonavir
	RAL - Raltegravir
	SQV - Saquinavir
	OTH - Other not pictured

B5. If yes, have you had any side effects from taking your current antiretroviral (ARV) medicines?

- 0 No
- 1 Yes
- 97 Don't Know
- 98 Refuse to Answer

B5a. If yes, what side effects did you have? Please list all the side effect you can think of, such as nausea, loss of appetite, vomiting, diarrhea, or any other symptom that you may have had. \_\_\_\_\_

B5b. Did you miss taking some or all of the doses of your current antiretroviral (ARV) medicines because of the side effects you experienced?

- 0 No
- 1 Yes
- 97 Don't Know
- 98 Refuse to Answer

B6. Are you currently taking anything else for your health such as vitamins, herbs, supplements or natural medicines?

- 0 No
- 1 Yes
- 97 Don't Know
- 98 Refuse to Answer

B6a. If yes, please list the name(s) of each vitamin, herb, supplement you are taking? \_\_\_\_\_  
-----  
-----

B7. Since your last study visit have you started taking traditional medicines that were recommended or provided by a traditional healer?

- 0 No
- 1 Yes
- 97 Don't Know
- 98 Refuse to Answer

B7a. If yes, please list the names of traditional medicines you are taking? \_\_\_\_\_  
\_\_\_\_\_

B7b. If yes, have you had any side effects from taking these traditional medicines?

- 0 No
- 1 Yes
- 97 Don't Know
- 98 Refuse to Answer

B7c. If yes, what side effects did you have? Please list all the side effect you can think of, such as nausea, loss of appetite, vomiting, diarrhea, or any other symptom that you may have had. \_\_\_\_\_  
\_\_\_\_\_

B8. (Ask of Women Only) Are you currently pregnant?

- 0 No
- 1 Yes
- 96 Not applicable, never been pregnant
- 97 Don't Know
- 98 Refuse to Answer

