### **Objective 3 Prospective Cohort**

From the group of donors identified as having incident and elite controller HIV infections, a smaller convenience group of willing participants will be enrolled into Objective 3 of the study. The planned study activities for Objective 3 participants are shown in Figure 3. Enrollment will take place at the time these donors attend the post-test HIV counseling visit, or, where the donors are not assessed to be ready for enrollment at that time, shortly thereafter.

Donors who agree to participate in the study will be fully consented as to the requirements of Objective 3 of the study. Donors who consent will then be enrolled on to the study and specimens collected for CD4, viral load and cytokine profiling as well as PBMC preparations. Samples will be labeled, packed and transported according to SANBS standard operating procedures which comply with all local requirements for the transportation of bio-hazardous material. All samples will be sent to the Donation Testing Laboratory in Constantia Kloof, Gauteng from where it will be sent to the appropriate laboratories for additional testing as required. Following sample collection, the participant will complete the ACASI questionnaire for Aim 1 of this study. In addition, at each follow-up visit a short questionnaire will be completed just after collection of the blood samples, using a Teleform-style form. The content of this questionnaire will assess healthcare-seeking behavior and any medicines or natural remedies the study participant has taken or initiated since the last study visit, possible side effects of these medicines and other exposures that may influence the viral dynamics of early HIV infection. Women will also be asked if they are currently pregnant.

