#### **4.6 Survey Considerations and OMB Requirements**

An extensive risk factor interview will be completed by both cases and controls who participate in this study (**Appendix 7**). Objective 3 participants will also complete a brief clinical questionnaire at each visit (**Appendices 8 and 9**). All interview instruments will have to be approved for use by OMB. We are planning to allow for up to nine months to obtain clearance to use the instruments.

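### The Objective 3 follow-up form (Appendix 8) records only part of the medicine use that the protocol says it will record, including continuing antiretroviral use

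*Protocol*

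**What the plan says.** The Objective 3 Prospective Cohort section sets the content of the short questionnaire completed at each follow-up visit. It is to assess "any medicines or natural remedies the study participant has taken or initiated since the last study visit, possible side effects of these medicines", and also "other exposures that may influence the viral dynamics of early HIV infection". Section 4.6 names the instrument (Appendices 8 and 9) and its timing: "Objective 3 participants will also complete a brief clinical questionnaire at each visit".

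Appendix 8 has three groups of medicine items.

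- **ARVs.** B4 asks "Since your last study visit have you started taking antiretroviral medicines, also known as ARVs". The answer No skips to B6. Otherwise B4a asks for the ARVs now being taken, B5 and B5a for side effects, and B5b for doses missed because of them.
- **Other products.** B6 asks "Are you currently taking anything else for your health such as vitamins, herbs, supplements or natural medicines". B6a follows: "If yes, please list the name(s) of each vitamin, herb, supplement you are taking".
- **Traditional medicines.** B7 asks "Since your last study visit have you started taking traditional medicines that were recommended or provided by a traditional healer", followed by names (B7a) and side effects (B7b, B7c).

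Items B1 to B3 ask about medical care, visits to a traditional healer, and infections since the last visit. They record reasons or symptoms.

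**The concern.** The protocol text makes three commitments: any medicine or natural remedy, whether used or begun since the previous visit, and its side effects. The form narrows each of them, and differently from item to item.

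Objective 3 is meant to characterise early viremia, antibody production and immune response through viral load, CD4 and cytokine measurements at enrollment and at 2, 3 and 6 months after the index donation. By setting these questions beside other exposures that may affect viral dynamics, the protocol gives its own reason for asking. If a medicine is never asked about, no later analysis can recover it, and a visit affected by it cannot be marked as such. ARVs matter most here, because they bear most directly on viral load.

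**Working it through.** The protocol gives no figure to reproduce, so the check is an item-by-item comparison of the stated content with Appendix 8.

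| Exposure | Items | Period asked about | Product named | Side effects |
|---|---|---|---|---|
| ARVs | B4 to B5b | Started since last visit; No skips to B6 | Current ARVs (B4a) | Yes (B5, B5a), plus missed doses (B5b), but only if not skipped |
| Vitamins, herbs, supplements, natural medicines | B6, B6a | Present use | Vitamins, herbs, supplements | None |
| Traditional medicines from a healer | B7 to B7c | Started since last visit | Yes (B7a) | Yes (B7b, B7c) |
| Conventional medicines other than ARVs | No dedicated item | None | No field | None |

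**Scope.** The last row is the gap in coverage. B6 has an open stem, but all its examples are non-conventional and B6a gives no place to name a conventional medicine.

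**Period.** A product taken and stopped between visits falls outside B6. A traditional medicine begun before the previous visit and continued falls outside B7, unless the participant reports it under B6.

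**ARV skip, traced through the visits.** Take a participant who starts ARVs between enrollment and the 2-month visit and continues them.

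1. At 2 months B4 is Yes, and B4a to B5b are asked.
2. At 3 months nothing has been started since the last visit, so No is a truthful answer. The form goes to B6, and regimen, side effects and missed doses are not asked.
3. At 6 months the same happens.

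One of three follow-up forms then carries ARV detail.

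**Other sources.** B1a records why care was sought, B2a why a healer was seen, and B3a the symptoms of an infection; none asks what was taken. In the Appendix 7 interview, L5, L6 and L8 concern ARVs without naming the drugs, and J20 concerns traditional medicine in the 6 months before donation. None of these covers medicines during follow-up.

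**Size of the cohort.** About 50 NAT-yield participants plus up to 20 elite controllers gives 50 + 20 = 70. With three follow-up visits each, that is at most 70 × 3 = 210 follow-up forms. This counts the forms in use, not the forms with missing information.

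**The case against.** Several points on the other side are sound.

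- **Episodes are not invisible.** B1 and B3 cover the interval since the last visit, so visits preceded by medical care or infection can be flagged. A reader might infer that treated episodes cannot be identified at all and would simply be taken for natural history. The form does not support that. What is lost is the identity of the medicine, and medicines taken without a care visit or a reported infection.
- **B6 is not strictly closed.** Its examples are illustrations, and some participants may mention a conventional medicine. It is therefore right to say that there is no dedicated item, and too strong to say that nothing could elicit such a medicine.
- **B7 does catch short courses.** One begun and finished between visits is a start and is within scope. B7 misses continuing use, part of which may surface under B6.
- **An ARV start can be carried forward** from an earlier form. That stands for the fact of starting, but not for whether treatment continued, with what regimen, side effects or missed doses.
- **Objective 3 is mainly descriptive** (section 4.9), which limits the consequence. It does not remove it, because description also needs to know which visits were affected.

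A reader might also infer that most short courses are missed. If one assumes a 7- to 14-day course placed at random in the interval, the chance that it is still current at the visit is 7/30 = 0.23 to 14/30 = 0.47 over one month, and 7/90 = 0.08 to 14/90 = 0.16 over three. The course lengths and timing are assumptions, and the protocol gives no rate of medicine use. These figures say nothing about how many exposures would actually be lost.

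**Conclusion.** The mismatch is real and lies within the protocol: Appendix 8 asks for less than the Objective 3 text says it will. It affects conventional non-ARV medicines (no dedicated item), supplements and natural medicines (present use only, no side effects), traditional medicines (new starts only) and ARVs (new starts only, with a skip that drops continuing users). ARVs should not be regarded as adequately covered; they are the most consequential instance.

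The consequence is partial recording of medicine exposure in a cohort of about 70. The amount of information lost cannot be estimated from the document. The conclusion assumes that participants answer the items as worded and that no other instrument collects medicine use during follow-up; the protocol shows none. This is a modest defect in a data-collection form, worth correcting because it is cheap now and cannot be repaired by analysis later.

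**What to change.** Reconcile Appendix 8 with the Objective 3 Prospective Cohort section before the form goes for OMB clearance.

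- **B4:** ask about ARVs taken or started since the last visit, so that B4a to B5b are put to everyone on ARVs.
- **B6/B6a:** ask about any other medicine, prescribed or bought, and any vitamin, herb, supplement or natural medicine taken since the last visit. Record its name and side effects.
- **B7:** ask about traditional medicines taken or started since the last visit.

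Use the answers to flag affected visits in the descriptive Objective 3 analysis. The cost is a few reworded or added items and a slightly longer form at each visit. Section 4.6 allows up to nine months for clearance of the instruments, so the change is easiest before submission.

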***Thank you for taking the time to complete this questionnaire. Please return this questionnaire to the research staff.***

***If you have any questions or concerns, please talk to the research assistant or nurse. You can also contact the medical director at our blood bank.***

Appendix 9 Placard Showing Antiretroviral Medicine Pictures

Generic name	Trade name	Formulation	Standard adult dose	Pills/day	Major side-effects	Food restrictions
Nucleoside reverse transcriptase inhibitors (NRTIs)						
3TC, lamivudine	Epivir	150* and 300mg tablets	150mg twice a day or 300mg once a day	2	Common: Nausea, vomiting, diarrhoea, headache, abdominal pain, hair loss, fever, insomnia (difficulty sleeping), rash, tiredness, runny nose, joint pain Rare: Lactic acidosis, liver damage	Take with or without food
Abacavir	Ziagen	300mg tablet	300mg twice a day or 600mg once a day	2	Common: Rash, nausea, vomiting, diarrhoea, fever, headache, tiredness, loss of appetite Rare: Hypersensitivity reaction, lactic acidosis	Take with or without food
AZT, zidovudine	Retrovir	100 and 250mg* capsules	250mg twice a day	2	Common: Nausea, vomiting, fatigue, headache, dizziness, weakness, muscle pain, loss of appetite, fever Rare: Blood disorders, lipodystrophy, lactic acidosis	Take with or without food
d4T, stavudine	Zerit	20, 30 and 40mg* capsules	People over 60kg: 40mg twice a day People under 60kg: 30mg twice a day	2	Common: Lipodystrophy, peripheral neuropathy, nausea, diarrhoea, abdominal pain, heartburn, dizziness, tiredness, rash, itching Rare: Pancreatitis, lactic acidosis	Take with or without food
ddI, didanosine	VidexEC	125, 200, 250 and 400mg* capsules	People over 60kg: 400mg once a day or 200mg twice a day People under 60kg: 250mg once a day or 125mg twice a day	1 or 2	Common: Peripheral neuropathy, nausea, vomiting, diarrhoea, abdominal pain, rash, headache Rare: Pancreatitis, lactic acidosis	Take at least two hours after and two hours before eating or drinking anything except water
FTC, emtricitabine	Emtriva	200mg capsule	200mg once a day	1	Common: Nausea, diarrhoea, headache, raised kinase levels, skin darkening in children Rare: Lactic acidosis, liver damage	Take with or without food
Nucleotide reverse transcriptase inhibitor (NRTI)						
Tenofovir	Viread	300mg tablet	300mg once a day	1	Common: Nausea, vomiting, diarrhoea, dizziness, low blood phosphate levels, weakness, rash, headache, stomach pains, fatigue, bloating, flatulence Rare: Kidney problems, bone thinning	Take with food
NRTI / NRTI fixed-dose combinations						
3TC / AZT	Combivir	Tablet comprising 150mg 3TC and 300mg AZT	One tablet twice a day	2	See 3TC and AZT	Take with or without food
3TC / abacavir / AZT	Tyzint	Tablet comprising 150mg 3TC, 300mg abacavir and 300mg AZT	One tablet twice a day	2	See 3TC, abacavir and AZT	Take with or without food
3TC / abacavir	Kivexa (EU)	Tablet comprising 300mg 3TC and 600mg abacavir	One tablet once a day	1	See 3TC and abacavir	Take with or without food
FTC / tenofovir	Truvada	Tablet comprising 200mg FTC and 300mg tenofovir	One tablet once a day	1	See FTC and tenofovir	Take with food
NRTI / NRTI / NNRTI fixed-dose combinations						
FTC / tenofovir / efavirenz	Atripla	Tablet comprising 600mg efavirenz, 200mg FTC and 300mg tenofovir	One tablet once a day	1	See FTC, tenofovir and efavirenz	Take on an empty stomach, preferably at bedtime
FTC / rilpivirine / tenofovir	Eviplexa	Tablet comprising 200mg FTC, 25mg rilpivirine and 300mg tenofovir	One tablet once a day	1	See FTC, rilpivirine and tenofovir	Take with a meal
Non-nucleoside reverse transcriptase inhibitors (NNRTIs)						
Efavirenz	Sustiva Stocrin	600mg tablet* and 200mg capsule	600mg once a day	1 or 3	Common: Rash, dizziness, sleep disturbance, abnormal dreams, impaired concentration, nausea, vomiting, headache, tiredness, diarrhoea, anxiety, depression Rare: Psychosis, severe rash, liver problems	Take on an empty stomach, preferably at bedtime
Etravirine	Integrale	100 and 200mg* tablet	200mg twice daily	2 or 4	Common: Rash, peripheral neuropathy Rare: Severe rash (Stevens Johnson syndrome)	Take with food
Nevirapine	Viramune	200mg tablet	200mg once a day for two weeks then 200mg twice a day	2	Common: Liver toxicity, allergic reaction, rash, nausea, headache, fatigue, stomach pain, diarrhoea Rare: Severe rash (Stevens Johnson syndrome)	Take with or without food
Nevirapine	Viramune prolonged-release	400mg tablet	400mg once a day after introductory period on non-extended-release nevirapine	1	Common: Liver toxicity, allergic reaction, rash, nausea, headache, fatigue, stomach pain, diarrhoea Rare: Severe rash (Stevens Johnson syndrome)	Take with or without food
Rilpivirine	Eduant	25mg tablet	25mg once a day	1	Common: Insomnia (difficulty sleeping), headache, rash, mood changes, depression Rare: At doses above 25mg may cause a disturbance to the heart rhythm	Take with a meal
Protease inhibitors						
Atazanavir	Reyataz	150, 200 and 300mg* capsule	300mg with 100mg ritonavir once a day or 400mg with 100mg ritonavir once a day with efavirenz or nevirapine	2 or 3§	Common: Nausea, diarrhoea, rash, stomach ache, headache, insomnia (difficulty sleeping), vomiting, hyperbilirubinaemia, lipodystrophy, liver toxicity, diabetes, heartburn, jaundice Rare: Kidney stones, abnormal liver function, changes in heart rhythm	Take with food
Darunavir	Prezista	400 and 600mg* tablet	600mg with 100mg ritonavir twice a day or 800mg with 100mg ritonavir once a day	3 or 4§	Common: Diarrhoea, nausea, rash, stomach pain, vomiting, headache, lipodystrophy, liver toxicity, diabetes, fever Rare: Abnormal liver function, changes in heart rhythm	Take with food
Fosamprenavir	Lexiva	700mg tablet	700mg with 100mg ritonavir twice a day	4§	Common: Raised lipids, nausea, vomiting, diarrhoea, rash, abdominal pain, headache, dizziness, tiredness, tingling around the mouth, changes in liver and pancreas function, lipodystrophy, liver toxicity, diabetes Rare: Severe rash, changes in heart rhythm	Take with or without food
Indinavir	Crixivan	100, 200 and 400mg* capsules	800mg three times a day	6	Common: Kidney stones, abdominal pain, lipodystrophy, nausea, vomiting, heartburn, diarrhoea, rash, headache, dizziness, dry skin and mouth, tiredness, insomnia (difficulty sleeping), liver toxicity, diabetes Rare: Liver abnormalities, changes in heart rhythm	Take one hour before or two hours after food or take with a light, low-fat snack
Lopinavir / ritonavir	Kaletra	Tablet comprising 200mg lopinavir and 50mg ritonavir	Two tablets twice a day or four tablets once a day	4	Common: Lipodystrophy, raised liver enzymes, nausea, vomiting, diarrhoea, abdominal pain, weakness, heartburn, headache, raised lipids, liver toxicity, diabetes Rare: Changes in heart rhythm	Take with or without food
Ritonavir	Norvir	100mg capsule and 100mg tablet*	Full dose: 600mg twice a day to 'boost' other PIs: 100 - 200mg once or twice a day	12 to 4	Common (at full dose): Raised lipid and liver enzymes, nausea, vomiting, diarrhoea, abdominal pain, headache, weakness, numbness around the mouth, bad taste in mouth, lipodystrophy, liver toxicity, diabetes Common (at low dose): Raised lipid levels Rare: Changes in heart rhythm	Take with food to avoid nausea
Saquinavir	Inviso	200mg capsule and 500mg tablet*	1000mg with 100mg ritonavir twice a day	6§	Common: Lipodystrophy, nausea, vomiting, diarrhoea, rash, tiredness, raised liver enzymes and lipids, liver toxicity, diabetes Rare: Changes in heart rhythm	Take within two hours of food
Tipranavir	Aptivus	250mg capsule	500mg with 200mg ritonavir twice a day	8§	Common: Nausea, diarrhoea, vomiting, abdominal pain, tiredness, headache, fever, liver abnormalities, rash, lipodystrophy, liver toxicity, diabetes, lipid increases, flatulence Rare: Bleeding in brain, changes in heart rhythm	Take with food
Fusion inhibitor						
T-20, enfuvirtide	Fuzon	Powder reconstituted in water	Injection of 90mg under the skin twice a day	-	Common: Injection-site reaction, respiratory tract infections, peripheral neuropathy, weight loss	No food restrictions
CCRS inhibitor						
Maraviroc	Celseltiv	150*, 300mg tablets	300mg twice a day or 150mg twice a day with all ritonavir-boosted PIs except tipranavir or 600mg twice a day with efavirenz or etravirine	2 to 4	Common: Nausea, diarrhoea, fatigue, headache	Take with or without food
Integrase inhibitor						
Raltegravir	ISENTRO	400mg tablet	400mg twice a day	2	Common: Headache, insomnia (difficulty sleeping) Rare: Severe rash, hypersensitivity reaction	Take with or without food

\*Formulation(s) shown. § Includes ritonavir capsule(s).

The editors have taken all reasonable care in the production of this publication. Neither NAM, nor the editors, can be held responsible for any inaccuracies or mis-statements of fact beyond their control. In case of information on any treatment or therapy does not represent an endorsement of that treatment or therapy by NAM or the editors. The information should always be used in conjunction with professional medical advice.

